## 2 PROTOCOL SYNOPSIS

STUDY NAME	A Post-market Multi-Center Retrospective-Prospective Study to Assess Long-term Clinical Outcomes of Non-melanoma Skin Cancer Patients Treated with eBx
PRINCIPAL INVESTIGATOR	[name], FACR
SITES	Up to 5 sites will participate
STUDY DESIGN	
This is a retrospective-prospective post-market, on-label, observational study. Patients who completed eBx treatment <math>\geq</math> 5 years ago since final treatment will be identified and any existing data in the patient's record will be collected in addition to conducting follow-up visits for long-term follow-up. The study will include 2 parts:
 
 
1. Retrospective Chart Review: Collect data from patient records who completed eBx treatment a minimum of five years prior to study onset. The history and demographic data will be retrospectively collected from up to 300 subjects previously treated with eBx for the treatment of NMSC.
 
2. Prospective Follow-up: Patients will either return for a minimum of five-year long-term follow-up visits or telehealth (video) for the investigators to assess the lesion site, document absence/presence of local recurrence and long-term skin toxicities after treatment.
 

SAMPLE SIZE	Up to 300 patients will return for follow-up a minimum of five years post eBx treatment.
STUDY OBJECTIVES	
 
1. To evaluate local recurrence of eBx treated lesions in subjects with a minimum of five-year follow-up.
 
2. Assess long-term skin toxicities.
 

PRIMARY EFFECTIVENESS ENDPOINT	Absence of local recurrence at $\geq$ 5-year follow-up at treatment site(s).
SECONDARY SAFETY ENDPOINT	Occurrence of long-term skin toxicities.
ESTIMATED STUDY PERIOD	Follow-up Visits: Estimated to occur over 6 months.
SPONSOR & FUNDING PARTY	
Xoft, Inc., a Subsidiary of iCAD, Inc.  [name]  [name]

STATISTICAL ANALYSES, STUDY MANAGEMENT, EDC, MEDICAL WRITING	
Eminence Clinical Research, Inc.  [name]  [name]  [name]

## 4 INTRODUCTION AND BACKGROUND

More than one million skin cancer cases occur annually. Most of these forms of skin cancers are curable. Carcinoma is a medical word for a cancer that starts in a lining layer of cells such as the skin or the lining cells of the digestive system. There are many types of keratinocyte cancer, but two types of epithelial skin cancers are most common, basal cell carcinoma (BCC) and squamous cell carcinoma (SCC).

Epithelial skin cancer is a common neoplasm that affects more than a half of a million people each year. The most serious of skin cancers is melanoma, which was diagnosed in approximately 60,000 people in 2007. However, the majority of these lesions, estimated to be eighty to ninety percent, are basal cell cancers and the remainder is categorized as squamous cell.

Both types of malignancies are related to ultraviolet light exposure from the sun. Basal cell cancer begins in the lowest layer of the epidermis, the basal cell layer. About eight out of ten skin cancers are BCCs. They usually begin on areas exposed to the sun, such as the head and neck. BCC was once found mostly in middle-aged or older people, in the fourth decade of life and beyond. But now it is also being seen in younger people. This may be because people are spending more time in the sun without protecting their skin. BCC tends to grow slowly. It is very rare for a basal cell cancer to metastasize. But if left untreated, it can grow into nearby areas and spread into the bone or other tissues beneath the skin.

SCCs are more likely to spread into fatty tissues just beneath the skin. They are also more likely to spread to lymph nodes or to distant parts of the body than are BCCs, but this is not common. With thorough screening these neoplasms can be identified at an early stage. With the selection of the appropriate treatment option, these cancers can result in excellent local control with excellent cosmesis results.

There has been a diverse variety of modalities developed for the treatment of basal cell and SCC over the years, from surgical excision to Mohs micrographic surgery, to radiation therapy. The location of the cancer and the extent of the disease effect the treatment options available to patients. The following section provides an overview of the different treatment modalities published in the literature.

Lovett et al reported on 339 patients who were consecutively treated for histologically confirmed basal cell (71%) and squamous cell (29%) carcinoma. A retrospective study was performed to assess local recurrence. The majority of the basal cell lesions (93%) and 97% of the SCCs were on the head. Radiation therapy was the initial treatment modality in 212 patients, and 127 patients were treated with radiation therapy after the initial surgical excision failed. Tumor control was analyzed by the type of external beam radiation therapy administered. The local control for superficial x-ray ranged from 91 to 100% reported categorically by tumor size.

Electron beam ranged from 70 to 75% local control. Patients were stratified into groups by the type of radiation beam used on the treatment. Excellent to good cosmesis was seen in 97% of the patients treated with superficial X-rays and in 78% of the patients treated with electrons, 78% of the patients treated with mixed beams, and in 80% of the patients treated with megavoltage photons. The overall complication rate (complications were defined as grade 4 toxicities) for the 310 patients whose data was available was 5.5%. Of the 217 previously untreated patients, the complication rate was 3.2%.

Silva et al report on a retrospective review of radiation therapy treatment for basal cell, squamous cell, and basal-SCC from 313 patients with 334 lesions treated. The objective of this study was to assess local control and late toxicities in patients treated with radiation therapy for the treatment of cancer of the pinna of the ear. For 270 patients, radiation therapy was the primary treatment, 50 patients received radiation therapy for recurrent cancer that had not previously undergone resection, and 12 patients received radiation therapy as an adjuvant treatment.

Other treatment options for patients with basal cell or SCCs include curettage, Mohs surgery and conventional surgery. Curettage has been said to be quick, requires minimal equipment, and is associated with a cure rate of 90% or better for select low-risk skin cancers. With this strategy, however, there is no margin control, and healing and cosmesis can be variable; moreover, it is not a very effective treatment for high-risk tumors and tumors in certain locations.

A common treatment for non-melanoma skin cancer (NMSC) has been Mohs surgery, which uniquely orients, maps, and processes removed tissue, permitting the microscopic evaluation of virtually 100% of the specimen margins. The completeness of this margin control permits the accurate identification and removal of all tumor extensions under the microscope. Tissues in Mohs surgery are processed as modified frozen sections which allow the accurate and rapid interpretation of most skin cancers. For those patients where surgical resection is not an option, primary treatment with radiation therapy was selected for patients whose data will be collected in this study. The treatment approach was individualized based on specific risk factors, and patient characteristics for the most acceptable cosmetic and functional outcome.

## 5 STUDY RATIONALE

Non-melanoma skin cancers, BCC and SCC, are the most prevalent of all skin cancers. Multiple publications have shown that radiation therapy using kilovoltage X-rays is a viable option for the treatment of BCC and SCC but treatment must be individualized to determine if radiation therapy should be an adjuvant therapy following surgical resection or if the radiation therapy is the primary treatment for skin cancer. Local recurrence rate varies depending on the histology, BCC versus SCC. SCC has a higher recurrence rate than BCC; deaths have been attributed to the recurrence of SCC.

Brachytherapy has the advantage of delivering a high dose to the tumor while sparing the surrounding normal tissues. With proper case selection and delivery technique, high-dose rate (HDR) brachytherapy has great promise, allows short treatment times, and can be performed on an outpatient basis. The Xoft Axxent Electronic Brachytherapy (eBx) System allows for the administration of high dose rate brachytherapy treatments using an electronic source. The Xoft Axxent System Controller and Source are cleared by the United States Food and Drug Administration to deliver high dose rate X-ray radiation for brachytherapy.

A matched pairs study was completed previously comparing eBx treatment outcomes to Mohs surgery outcomes. The median follow-up was three years. Local recurrence, toxicities, and cosmesis were the endpoints. Because of the excellent cosmetic outcomes evident in this study at three years, the physicians rated cosmesis as “excellent” or “good” in 97.6% of EBx-treated

lesions, and 95.7% of MMS-treated lesions, cosmetic outcomes in this study will not be collected. It is most important to understand the long-term recurrence rates for this treatment option. The rationale for this retrospective data collection study is to understand longer-term outcomes in patients treated with eBx for the treatment of both BCC and SCC NMSC.

## **6 STUDY PURPOSE**

The purpose of this retrospective-prospective study is to evaluate lesions after treatment for BCC or SCC NMSC in order to gain a better understanding of the durability of the treatment, and risk of late toxicities for this patient population.

## **7 STUDY DESIGN, ENROLLMENT, AND DURATION**

### **7.1 Study Design**

This is a retrospective-prospective study design. The study is post-market, on-label observational study for the treatment of NMSC. Patients who completed treatment at least five years from the last treatment will be identified and existing data as required by this protocol in the patient's record will be collected in addition to conducting office visits or telehealth visits (video) for long-term follow-up.

The study will include:

Identifying patients, retrospectively, who completed treatment a minimum of five years from the last treatment. The history and demographic data will be collected from up to 300 subjects previously treated with eBx for the treatment of NMSC. Patients will have an office visit or telehealth visit in order for the investigators to assess the lesion site, document absence of recurrence, treatment for recurrence (if applicable), and long-term toxicities at the time of the prospective visit.

### **7.2 Sample Size**

Up to 300 subjects treated with eBx will have data collected retrospectively from the patient's medical records, and prospectively at the time of the follow-up visit for those who agree to participate in this study. Up to three lesions per subject may be included in this study. The sample size will include those who were treated previously with eBx per the standard of care treatment as published in Patel et al and Doggett et al.

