## **8.2 Long-term Follow-up Visits**

Patient Selection: Patients who are due for their annual skin assessment with a minimum of five years since their last eBx treatment will be selected to call for an appointment. The patients who were in prior studies will be called from a list kept at the study sites. Additional patients who were not in the previous studies will be contacted if they meet eligibility criteria. The patient will be told about the study and asked if they would be willing to participate in the Xoft study through an on-site or remote telehealth appointment.

On-site Visits: Patients agreeable to participating that return for an office visit for prospective data collection will be offered \$100.00 compensation for his/her time and effort required to participate in this study. Written informed consent will be required for participation in the study.

Remote Visits: Patients agreeable to participating that choose a remote visit by video, such as Zoom or Web-Ex or another video conference platform will be offered \$100.00 compensation for his/her time and effort to participate in this study. Verbal informed consent documented by the study staff will be required for participation in the study. Signed informed consent will be waived.

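### Sections 7.2 and 8.2 say who may be called, but not that all eligible patients must be called or in what order, so the text leaves room for outcome-aware choice of who enters the recurrence percentage

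*Combined protocol and SAP*

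**What the plan says.** **Numbers.** The synopsis (Section 2) says of the chart review: "The history and demographic data will be retrospectively collected from up to 300 subjects previously treated with eBx". Its sample-size row says: "Up to 300 patients will return for follow-up a minimum of five years post eBx treatment". Section 7.2 joins the two: "Up to 300 subjects treated with eBx will have data collected retrospectively from the patient's medical records", and also "prospectively at the time of the follow-up visit for those who agree to participate in this study". The synopsis allows up to five sites.

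**Selection.** Section 8.2 gives three statements: "Patients who are due for their annual skin assessment with a minimum of five years since their last eBx treatment will be selected to call"; "The patients who were in prior studies will be called from a list kept at the study sites"; and "Additional patients who were not in the previous studies will be contacted if they meet eligibility criteria". Section 12.1 ties the on-site appointment to the next clinic visit that the payer requires.

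**What sites may know.** Section 8.1 begins with a review of the site's own records for eligibility and analysis variables. Section 11.1 draws the sites from those in the matched-pair study, and Section 5 names local recurrence among that study's endpoints, with a median follow-up of three years.

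**What is reported.** Section 13.2 says the study is not powered and exists to give the count and percentage of subjects with a recurrence and with a late skin toxicity. Section 11.5 supplies a Subject Screening Log without saying what it must contain.

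**The concern.** In a descriptive study with no comparator and no test, the percentage is the result, and its validity rests on who is in the denominator. The protocol defines a group that may be called but gives no rule for working through it.

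This matters more than usual because the outcome may already have happened. Section 8.1 counts a recurrence before the study visit as outcome data, so an event on file at the site is part of the endpoint. If that knowledge influences who is telephoned, the percentage shifts. It could fall, if patients with a known recurrence are passed over. It could rise, if they are easier to reach because they attend more often. Without a record of everyone who could have been called, the shift can be neither detected nor corrected at analysis.

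The point concerns the site's choice of whom to approach. Refusal, death and loss to follow-up are a separate matter.

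**Working it through.** **1. Is there a figure to reproduce?** No. The 300 is a ceiling with no derivation, and Section 13.2 declares the study not powered.

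**2. What the selection text fixes and leaves open.**

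| Element | In the protocol? |
|---|---|
| Minimum time since last eBx | Yes, five years (8.2) |
| Timing of the call | Yes, patients due for a yearly skin check (8.2); on-site visit aligned with the next clinic visit (12.1) |
| Sources of patients | Yes, prior-study list and other eligible patients (8.2) |
| Duty to call everyone eligible | No |
| Order of calling, within or between sources | No |
| Share of the 300 by site | No |
| Who is left out once 300 is reached | No |
| Report of numbers eligible and called | No (13.2; log content undefined in 11.5) |

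**3. Can an outcome be known before the call?** Yes, in two ways. Sites read their own records first (8.1). To the extent that the site-held list comes from the matched-pair study, recurrence in those patients was already assessed (5, 11.1).

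**4. Size of the possible shift (illustration).** Let p be the true recurrence proportion and r the chance of being called for a patient with a known recurrence, relative to one without. Treat every recurrence as known to the site, and suppose that patients, once called, agree and are seen at the same rate whatever their outcome. The expected percentage is then

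r·p / (r·p + 1 − p).

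The values of r are assumptions. The main case p = 5% is also an assumption. It is bracketed by two figures from Section 4: 2% (100 − 98, from the five-year control in the surface-mold HDR series) and 9% (100 − 91, from the lower end of control with superficial X-rays).

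| True p | r = 0.5 | r = 0.75 | r = 1 | r = 2 |
|---|---|---|---|---|
| 2% | 0.010/0.990 = 1.0% | 0.015/0.995 = 1.5% | 2% | 0.04/1.02 = 3.9% |
| 5% | 0.025/0.975 = 2.6% | 0.0375/0.9875 = 3.8% | 5% | 0.10/1.05 = 9.5% |
| 9% | 0.045/0.955 = 4.7% | 0.0675/0.9775 = 6.9% | 9% | 0.18/1.09 = 16.5% |

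**5. Scale.** With 15 recurrences in 300 (5%), the exact 95% interval is 2.8% to 8.1%. Both 2.6% and 9.5% lie outside it; 3.8% lies inside. At a true 5%, a factor of two in either direction would exceed the sampling error of the largest permitted study.

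**6. What the cap adds.** Let N be the number eligible, R = 0.05·N the recurrences among them, and 300 the number seen. The lowest possible percentage is max(0, R − (N − 300))/300 and the highest is min(300, R)/300.

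- N = 300 (R = 15), all called and all agreeing: 15/300 = 5%. No distortion.
- N = 400 (R = 20): from max(0, 20 − 100)/300 = 0% to 20/300 = 6.7%.
- N = 600 (R = 30): from max(0, 30 − 300)/300 = 0% to 30/300 = 10%.

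The documents do not give N. These are logical limits, not forecasts.

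**The case against.** **Selection is not open-ended.** Section 8.2 sets a minimum interval, a due-date trigger and the sources of patients. A due date has no obvious link to anyone's preference. This stands: a reader who inferred that nothing governs who is called would be wrong. But a due date defines a pool. It does not say that all of the pool is called, or in what order.

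**The two limits of 300 do not conflict.** A reader might infer a contradiction, with 300 visits reachable only by replacing refusals. The documents do not support that. The figure is a ceiling, fewer visits breach nothing, and no replacement is mentioned. Consent is an inclusion criterion (7.6.1), so the same 300 consented patients could each have a chart and a visit. What remains is an ambiguity in Section 7.2, where visits are for those who agree.

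**Recurrence is not part of the chart review.** Section 8.1 and Table 1 place it, including earlier recurrence, under prospective collection. This stands: no section says that staff look at recurrence before calling, or that sites choose freely. The text permits such choice by silence, and nothing suggests that any site intends it.

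**The pool may be small.** With 300 or fewer eligible, the cap excludes nobody. This also stands, but the missing duty to call everyone remains.

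**Consecutive enrolment is not the protocol's own benchmark.** Section 4 describes one cited series as covering "patients who were consecutively treated for histologically confirmed basal cell" and squamous cell carcinoma. It is one of several and is not named as a comparator, so no weight is placed on it here.

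**Conclusion.** The concern holds in a limited form. The protocol says who may be called. It does not require that everyone be called, fix an order, share the places among sites, or require the eligible pool to be reported. Sites that hold the records, and that took part in a study with recurrence as an endpoint, therefore have discretion at a stage where an outcome can already be known.

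At an assumed true 5%, the expected percentage would be 2.6%, 3.8% or 9.5% if patients with a known recurrence were half, three quarters or twice as likely to be called. These figures rest on assumed values of r and on equal participation once called. They show how sensitive the result is; they do not estimate a bias that has occurred. The wider 0% to 10% range should not be read as a likely result: it needs an assumed pool of 600 and the exclusion, or inclusion, of every recurrence.

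The protocol should be changed before calling begins, because the problem cannot be repaired at analysis.

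**What to change.** Amend Sections 7.2 and 8.2:

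1. Before any contact, each site lists every eBx patient who meets the chart-based criteria, with no cap on the list.
2. The CRO fixes the calling order before recurrence information is reviewed, either consecutive by date of last eBx or computer-random within site. The order applies among patients who fall due for assessment in the visit period, so the scheduling in Sections 8.2 and 12.1 can stay.
3. Sites call in that order, always taking the next name, until everyone has been called or 300 in total have consented. The protocol also states how the places are shared among sites, for example in proportion to list length.
4. Section 7.2 and the synopsis state that the 300 applies to consented visits. The final report gives, by site and from the Subject Screening Log, the numbers eligible, called, reached, refused and seen.

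**Cost.** Protocol wording, one ordered list per site, and somewhat less freedom in scheduling calls. The log already exists. Patients on the list who do not fall due in the estimated six-month visit period would be recorded as not due, so the reader can see how much of the pool the study covers. The change does not deal with refusal, death or loss to follow-up, though the counts in item 4 would show the refused and unreached.

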### **7.3 Study Objective**

Evaluate long-term local recurrence ( $\geq 5$  years post-treatment) of eBx treated lesions at follow-up.

### **7.4 Primary Effectiveness Endpoint**

Absence of local recurrence at  $\geq 5$ -year follow-up at treatment site(s).

## 7.5 Secondary Safety Endpoint

Occurrence of long-term skin toxicities at the prospective follow-up visit.

## 7.6 Eligibility Criteria

**7.6.1 Inclusion Criteria** All answers must be YES to have lesions included in this study.

1. Previously completed treatment for non-melanoma skin cancer using Xoft eBx Electronic Brachytherapy System according to standard of care;
2. Provides informed consent;
3. Greater than 40 years of age;
4. Pathological diagnosis confirmed to be squamous cell carcinoma, or squamous cell carcinoma-in-situ, or basal cell carcinoma prior to treatment;
5. Cancer Staging included in this study:
  - Stage 0: Tis, N0, M0
  - Stage 1: T1a, b, c, N0, M0
  - Stage 2: T2a, N0, M0

### 7.6.2 Exclusion Criteria

All answers must be NO to have lesions included in this study.

1. Target area is adjacent to a burn scar;
2. Any prior definitive surgical resection of the cancer, prior to Radiation Treatment;
3. Known perineural invasion;
4. Actinic Keratosis;
5. Known spread to regional lymph nodes;
6. Known metastatic disease;
7. Lesion treated with Mohs surgery.

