## 8 METHODOLOGY

### 8.1 Identifying the Population

The first phase of this study will be to identify patients who completed treatment with eBx at least five years ago prior to study onset and collect history and demographic data, and eligibility data retrospectively from the patient records and on source worksheets.

This phase will include a review of the site's medical records to determine if the source documentation contains the variables that are needed to determine eligibility, and which will be used in the endpoint analyses.

These variables include:

Patient Age

Pathology report for evidence of:

- o Lesion size (cm) / TNM stage
- o Lesion diagnosis (BCC, SCC)

Last treatment date for each location

Lesion location (e.g. face, extremities, neck, nose, scalp, torso)

Data Collected Prospectively:

Recurrence of cancer at prospective follow-up visit

Recurrence occurred prior to prospective follow-up visit

Long term skin toxicity (graded according to CTCAE v.5)

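### The background describes primary radiation treatment, but eligibility bars only prior resection and Mohs surgery, and no named variable identifies lesions treated another way before eBx

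*Combined protocol and SAP*

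**What the plan says.** **Intended population.** Section 4 states that "primary treatment with radiation therapy was selected for patients whose data will be collected in this study", for patients in whom surgery was not an option.

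**Eligibility.** Two items in section 7.6.2 concern earlier treatment of the lesion: "Any prior definitive surgical resection of the cancer, prior to Radiation Treatment" (item 2) and "Lesion treated with Mohs surgery" (item 7). No item mentions prior radiation, topical treatment, curettage or recurrent lesions. Inclusion 1 in section 7.6.1 reads "Previously completed treatment for non-melanoma skin cancer using Xoft eBx Electronic Brachytherapy System according to standard of care", and standard of care is given by citation only. The glossary does not define definitive surgical resection.

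**Data.** Section 8.1 lists age, lesion size or stage, diagnosis, location and "Last treatment date for each location" as the chart variables. Prior treatment of the site and primary or recurrent status are not named. Table 1 includes a Demographics and History form, but its fields are not shown.

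**Analysis.** Section 13.2 plans descriptive counts and percentages by subject and by lesion, with no split by treatment history. Section 7.5 counts late skin toxicity seen at the visit, without attribution to a particular treatment.

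**The concern.** Section 6 gives the purpose as the durability of the treatment and the risk of late toxicity. For a lesion that had already failed another treatment, both outcomes partly reflect what happened before eBx. The tumour has shown that it can recur, and late skin change may come from the earlier treatment, from eBx, or from both.

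The study has one arm and tests no hypothesis, so its percentages are its whole product. Their meaning depends on knowing which lesions they describe. If previously treated lesions are mixed in and not flagged, a reader who takes the results as those of primary treatment may be misled, and no planned table would show it.

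**Working it through.** The plan states no figure on this point, so there is nothing to reproduce. The check sets the provisions side by side and then uses the protocol's own background for scale.

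**1. Does the text let such lesions in?** By type of treatment before eBx:

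| Prior treatment of the site | Excluded by section 7.6.2? |
|---|---|
| Definitive surgical resection | Yes, item 2 |
| Mohs surgery | Yes, item 7 |
| Curettage | Unclear |
| Topical treatment | No item |
| Radiation | No item |

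Curettage is unclear because section 4 lists it apart from conventional surgery ("Other treatment options for patients with basal cell or SCCs include curettage, Mohs surgery and conventional surgery") and the term in item 2 is undefined. Section 8.2 also allows patients who were not in the earlier studies, so the criteria of those studies do not close the gap.

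**2. Could the analysis identify them?** Only if the history form happens to ask. Nothing in section 8.1 requires it, and section 13.2 does not use it.

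**3. Does the group exist?** In the cited series on the pinna of the ear (section 4), "50 patients received radiation therapy for recurrent cancer that had not previously undergone resection". The three groups given are 270 + 50 + 12 = 332, so 50/332 = 15.1%. The total of 332 exceeds the stated 313 patients and is close to the 334 lesions; those denominators give 16.0% and 15.0%.

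**4. Could outcomes differ?** In the 339-patient series (section 4), complications occurred in 5.5% of 310 patients. "Of the 217 previously untreated patients, the complication rate was 3.2"%.

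- All: 0.055 × 310 = 17.05, about 17 events.
- Previously untreated: 0.032 × 217 = 6.94, about 7 events.
- Remainder: (17 − 7)/(310 − 217) = 10/93 = 10.8%, and 10.8/3.2 is about 3.4 times the untreated rate.

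The same series is also described as having 212 patients with radiation as initial treatment. With 212, the remainder is (17.05 − 6.78)/98 = 10.5%.

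**5. Illustration for toxicity.** Pooled rate = (1 − f) × 3.2% + f × 10.8%, where f, the previously treated share, is an assumption.

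| f | Pooled rate | Expected among 300 |
|---|---|---|
| 0% | 3.2% | 9.6 |
| 5% | 3.6% | 10.7 |
| 10% | 4.0% | 11.9 |
| 15% | 4.3% | 13.0 |
| 30% | 5.5% | 16.4 |

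**6. Illustration for recurrence.** The base is 2%, from the 98% five-year local control in the cited surface-mold brachytherapy series. The risk ratio RR is purely assumed. Pooled rate = 2% × [(1 − f) + f × RR]. At f = 15% this gives 2.3%, 2.6% and 3.2% for RR of 2, 3 and 5, so 6 events in 300 become 6.9, 7.8 and 9.6.

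**7. Against sampling error.** The exact 95% interval is 0.7% to 4.3% for 6/300 and 1.6% to 6.0% for 10/300. At shares up to 15%, the shifts in steps 5 and 6 lie inside these intervals.

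**The case against.** The strongest reply is that the population is already as intended. Section 5 contrasts primary radiation with adjuvant radiation after resection. On that reading, exclusions 2 and 7 deliver primary treatment, and the sentence in section 4 is background narrative. This is arguable. Section 4 itself, however, separates primary from recurrent cases when it describes the pinna series, so the protocol uses the word in more than one sense and a site cannot tell which applies.

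Inclusion 1 and section 7.2 also tie treatment to published standard of care, which may have been limited to new lesions. That cannot be settled from the documents.

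A reader might go further in four ways that the documents do not support:

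- **That such lesions do enter, at about 15%.** The text shows only that they can. The 15% is from one anatomical site and a mainly orthovoltage series, and says nothing about these eBx sites.
- **That toxicity would be overstated by about a third** (4.3/3.2 = 1.35). The 10.8% behind this belongs to a group that the background describes as irradiated after failed excision, which exclusion 2 removes. It also counts grade 4 events after external beam, whereas section 9 expects mainly mild changes and records all of them.
- **That recurrence is shown to be biased.** The documents give no recurrence rate by treatment history.
- **That the data could never be separated.** The list in section 8.1 is not stated to be exhaustive, and the history form might ask. The supported statement is that nothing requires it.

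It also stands that the study is descriptive and unpowered, and that no stated figure becomes wrong. The sampling-error point limits the urgency, but a mixture shift is systematic: enrolling more patients does not remove it.

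**Conclusion.** The point holds as a mismatch between the population described in section 4, the criteria in section 7.6, the variables in section 8.1 and the pooled reporting in section 13.2. Lesions previously treated with radiation or topical agents can enter unidentified, and so, on one reading, can lesions treated by curettage. Their history could then be counted in both endpoint percentages.

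The size is unknown. The illustrations (3.2% becoming 4.0% to 5.5% for toxicity at shares of 10% to 30%; 2% becoming 2.3% to 3.2% for recurrence at a 15% share) rest on assumed shares, a proxy complication rate and assumed risk ratios. They show that the effect need not be trivial; they do not estimate it. The change is worth making because it is cheap and settles what the results describe.

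**What to change.** 1. **Section 8.1 and the Demographics and History form:** add one chart-abstracted item per lesion, any treatment of this site before eBx: none / curettage or destruction / topical / radiation / other / unknown.
2. **Section 13.2:** keep the all-lesion percentages. Also report recurrence and late toxicity for lesions with no prior treatment, with prior treatment and with unknown history. Tie any statement about primary treatment to the no-prior-treatment row. For the by-subject tables, state how a subject whose lesions have different histories is classified.
3. **Sections 4 and 7.6.2:** reconcile them on whether previously treated lesions belong to the study population, and define definitive surgical resection so that sites classify curettage alike.

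The cost is one more abstracted item and a few table rows. Charts at least five years old will leave some lesions with unknown history. For that reason, the split is better placed beside the all-lesion figures than used to make never-treated lesions the main analysis set.
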